9. STATISTICAL ANALYSIS

9.1 Biostatistical analysis

This is a crossover randomized controlled trial with the goal of determining the effects of a potential cognitionenhancing dietary supplement for older adults with SCD and MCI. The primary analysis will be based on an intention to treat approach and will include all subjects randomized at the onset of the trial to either NR then placebo or placebo then NR as described below.

In this study, the participants will pass through intervention blocks with administration of both NR and PBO for eight weeks administered in random order. The primary cognitive outcome measure will be the Total Scale score of the RBANS which will be administered at Baseline (Day 28), Crossover (Day 84), and End of Study (Day 140). The RBANS is a robust 25-minute, standardized neurocognitive battery with multiple alternate versions whose 12 subtests yield five Index scores, one for each cognitive domain, and the Total Scale score.

A Crossover, Randomized Block Sequence, Double-Blind, Placebo-Controlled Trial for Nicotinamide Riboside in Subjective Cognitive Decline and Mild Cognitive Impairment in Aging

Version:4.4

Normative data have been published for cognitively normal older adults, as well as for MCI and AD populations. For example, in a study of MCI, the mean Total Score Index was reported to be 92.4 with a standard deviation of 9.1⁴³. Based on test-retest reliability, a minimal detectable change in community-dwelling older adults (including normal, MCI and mild dementia) for the Total Score is 5⁴³. A "minimum clinically important difference" in MCI was reported to be 8 points⁴⁴.

The basic data of a crossover trial are the measurements obtained in 2 or more different intervention conditions occurring over time. The principal goal is to compare outcomes for each condition within a randomized block structure while accommodating repetition *within* subjects and possible effects of carryover or disease progression.

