Assessment of normality of data distribution will be completed prior to inclusion in any analysis. If the distribution of the outcome variables (e.g., RBANS Total Score, etc) are not normal, appropriate transformations (e.g., logarithm, square-root, Box-Cox transformation, etc) will be applied. Data analysis at the individual and group levels for the primary outcome will begin with visual inspection of RBANS Total Scores at each assessment for differences from baseline for each measurement and differences between intervention conditions. Ignoring potential for carryover, a simple matched pair t-test will be performed using data from each condition. Should carryover effects or other time trends be suspected, we can use a regression model adjusting for sequence.

Mixed-effects models will be used to compare the scores at the end of each study period (Days 28, 84, and 140) between NR and PBO incorporating variance within and between participants. This within-patient level will accommodate variation resulting from the intervention crossovers as well as time effects modeled in various forms (e.g., linear and non-linear trends, carryover effects). Each within-subject regression coefficient will be treated as a random effect that can vary based on these between participant factors. The primary analysis will calculate the average intervention effect (i.e., will model the mean of the individual intervention effects as a constant). Secondary analyses will model the mean as a function of factors that vary among patients such as age and sex. These terms describe the main effects of these factors, their interactions with the intervention, and their interaction with time. The analysis will be completed using SAS PROC MIXED through a restricted maximum likelihood analysis with a mixed model with fixed effects for sequence and treatment. Appropriate covariance structure will be investigated using Akaike's information criterion (AIC).

The full multilevel model will estimate both average effects across the population of participants, as well as effects for individuals informed by the results on other participants. The predicted effects for an individual participant are weighted averages of his or her data and the averages from others. This model incorporates correlations among the measurements within an individual and enables comparison of the individual's predicted intervention effect using the multilevel model with that from using only that individual's data.

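### The RBANS mixed model names only sequence and treatment and leaves Day 28 uncoded; if Day 28 is pooled with placebo, part of any practice gain is credited to NR.

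*Combined protocol and SAP*

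**What the plan says.** All of this is in Section 9.1 (Biostatistical analysis) unless noted.

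- **Model.** Mixed-effects models will "compare the scores at the end of each study period (Days 28, 84, and 140) between NR and PBO". The only concrete specification is a "restricted maximum likelihood analysis with a mixed model with fixed effects for sequence and treatment", with the covariance structure to be chosen by AIC.
- **Time.** The within-patient level is to accommodate "time effects modeled in various forms (e.g., linear and non-linear trends, carryover effects"). No form is selected, and none appears in the list of fixed effects. Also, "Each within-subject regression coefficient will be treated as a random effect".
- **Day 28.** The RBANS is "administered at Baseline (Day 28), Crossover (Day 84), and End of Study (Day 140"). The first look at the data covers "differences from baseline for each measurement and differences between intervention conditions". Section 3.1 puts a four-week placebo lead-in for all volunteers before the two 8-week blocks, so Day 28 is also the end of a placebo period.
- **Simpler analyses.** The plan starts with an unadjusted paired comparison: "Ignoring potential for carryover, a simple matched pair t-test will be performed using data from each condition". It then offers an adjustment, worded as an option and triggered only by suspicion: "Should carryover effects or other time trends be suspected, we can use a regression model adjusting for sequence".
- **Practice.** Section 9.1 accepts that practice effects cannot be ruled out and may be hard to gauge on the RBANS. Section 7.1.2.2.3 specifies alternate forms at the three visits.
- **Status.** All outcomes are described as exploratory, without claims, and P below 0.05 is to be called significant.

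**The concern.** The text supports more than one coding of Day 28. Listing it among the period ends compared between NR and placebo, after a placebo lead-in, invites entering it as a placebo response. Calling it Baseline points the other way. Nothing settles the matter.

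The choice matters because nobody takes NR before Day 28. If Day 28 is an ordinary placebo score, placebo includes every first test and NR includes none, so treatment is partly confounded with test occasion. Counterbalancing does not repair this, since both sequences share the same first visit. A sequence term does not repair it either: it is a between-subject contrast and cannot absorb a within-subject trend over visits. A practice gain would then appear as an NR benefit when NR does nothing, and a decline over time would appear as harm.

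With both the coding and the time term open, the primary estimate depends on a choice that could be made after the data are seen.

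**Working it through.** The plan gives no sample-size, power or bias figure to reproduce. The check is the expected NR minus placebo estimate when the true NR effect is zero.

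**Inputs.** N = 40 (Section 3.1). Two counterbalanced sequences (Section 5.3), taken as 20 each. SD 9.1 (Section 9.1). Within-subject correlation r and practice gain are assumed. Mean gains at Days 28, 84 and 140 are 0, g1, g2: linear (0, g, 2g) or plateau (0, g, g). With Day 28 pooled, the NR codes are (0, 1, 0) for NR-first and (0, 0, 1) for placebo-first.

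**Day 28 pooled with placebo, sequence + treatment, compound symmetry.** Everyone has one NR score and two placebo scores, so the estimate is the mean over subjects of NR score minus the average of the two placebo scores.

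- NR-first: g1 − (0 + g2)/2
- Placebo-first: g2 − (0 + g1)/2
- Average at 20/20: (g1 + g2)/2 − (g1 + g2)/4 = (g1 + g2)/4

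Linear: (g + 2g)/4 = 0.75g. Plateau: (g + g)/4 = 0.50g. Neither depends on r.

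**Other structures.** These use the exact generalized least squares expectation (ΣX′V⁻¹X)⁻¹ ΣX′V⁻¹μ at 20/20.

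| Model | Linear, per point of g | Plateau, per point of g |
|---|---|---|
| Pooled, compound symmetry | 0.750 | 0.500 |
| Pooled, AR(1), r = 0.7 / 0.8 / 0.9 | 0.426 / 0.393 / 0.362 | 0.370 / 0.357 / 0.345 |
| Pooled, AR(1), plus random treatment coefficient (SD 1 to 4) | 0.374 to 0.470 | 0.306 to 0.369 |
| Pooled, plus fixed linear time | 0 | 0.154 (compound symmetry); 0.176 to 0.180 (AR(1)) |
| Day 28 with its own level, or left out | 0 | 0 |
| Categorical visit (or period) | 0 | 0 |

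The random treatment coefficient leaves the compound-symmetry values unchanged.

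**Unequal completers.** With Days 84 and 140 only and a 1-point gain between them, the NR minus placebo difference is −1 in NR-first and +1 in placebo-first. At 20/16 the raw mean is (−20 + 16)/36 = −0.111, and the sign reverses at 16/20. Giving Day 28 its own level yields −0.111 under compound symmetry and −0.093 to −0.099 under AR(1). Regressing the paired Day 84/140 difference on sequence, coded −1/+1, gives (−1 + 1)/2 = 0. On that reading the plan's optional adjustment is a valid period adjustment. If the paired analysis instead averaged Day 28 with the later placebo score, the sequence means under a linear gain are 0 and 1.5g. Their average, 0.75g, survives regression on sequence (0.50g for a plateau).

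**Standard errors, compound symmetry, r = 0.8.** 9.1² = 82.81.

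- Pooled, no visit term: √(1.5 × 82.81 × 0.2 / 40) = 0.788
- Categorical visit: √(2 × 82.81 × 0.2 / 40) = 0.910

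The ratio is √(2/1.5) = 1.155, about 15% at any r. Under AR(1) at r = 0.8 the rise is 0.765 to 0.844, and over r = 0.6 to 0.9 it is 10 to 11%.

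**The case against.** The strongest reply is that Day 28 is a baseline. The protocol repeatedly calls it that, the lead-in is described as acclimatization, and the compared conditions are the two 8-week blocks. A matched-pair test naturally takes one NR and one placebo score per person. On that reading the bias is 0 with balanced sequences. This stands as the more natural reading of much of the text, but the sentence defining the mixed-model comparison lists Day 28 alongside the other two days, and nothing excludes it as a placebo response.

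Second, time effects are promised, and the PROC MIXED sentence may be only a summary. It is fair to say that time is not ignored, but no form is committed to. A linear trend, one of the plan's own examples, leaves 0.15 to 0.18 of a plateau gain.

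Third, the size depends on the covariance. Random time slopes, which the plan may intend, shrink the pooled bias. Under compound symmetry at r = 0.8 with no fixed time term, linear/plateau falls to 0.58/0.43 (assumed slope SD 2) or 0.34/0.34 (SD 4). At r = 0.95 and slope SD 4 it is about 0.13/0.25. So high an r is plausible. If the quoted 5-point detectable change is a 90% or 95% value (level not stated, and the populations differ), the error SD is 5/(1.645√2) = 2.15 or 5/(1.96√2) = 1.80, and 1 − (error SD/9.1)² is 0.94 or 0.96. The compound-symmetry standard errors at r = 0.95 would then be 0.39 and 0.46. All of this changes the size of the bias; none of it removes the bias.

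Finally, alternate forms may make practice small, and the outcomes are exploratory. Both lower the stakes.

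**Conclusion.** The concern holds. The named model has no visit or period term, the coding of Day 28 is not stated, and one coding the text supports gives a biased primary estimate even with balanced sequences. Under pooling, the bias per point of gain is 0.75 (linear) or 0.50 (plateau) with compound symmetry, and 0.34 to 0.43 with AR(1) at r from 0.7 to 0.9. It is smaller if random time slopes are fitted. Choosing the covariance by AIC would therefore itself move the answer. Under the baseline reading the problem shrinks to 0 when balanced, and to 0.09 to 0.11 per point of gain between Days 84 and 140 at 20/16 or 16/20 completers without a period term.

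The size in this trial is unknown, because the documents give no practice gain. As an illustration only, an assumed plateau gain of 1 to 3 points gives a bias of 0.5 to 1.5 points (compound symmetry) or 0.3 to 1.1 (AR(1)). That is below the 5-point detectable change and 8-point important difference quoted in Section 9.1. The 5-point figure rests on test-retest reliability, so it is an individual-level threshold and a loose yardstick for a group mean. Against the pooled standard error of 0.79 at r = 0.8, 1.5 points is 1.5/0.79 = 1.9 standard errors.

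Given the exploratory status, this should be fixed but is not critical.

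**What to change.** Before unblinding, amend Section 9.1 to:

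1. State how Day 28 enters the primary model.
2. Add categorical visit as a fixed effect alongside sequence and treatment, or categorical period if only Days 84 and 140 are responses. Using Day 28 as a covariate is optional.
3. Move linear, non-linear and other forms of time to named sensitivity analyses.
4. State that the matched-pair t-test uses Days 84 and 140 only, and that adjusting for sequence means regressing the paired NR minus placebo difference on sequence.

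This is a wording change and needs no new data. The precision cost applies only if Day 28 would otherwise have been pooled with placebo: 0.79 to 0.91 points (compound symmetry) or 0.77 to 0.84 (AR(1)) at SD 9.1 and r = 0.8. If Day 28 is already outside the response vector, adding period leaves the standard error at 0.91 with 20 per sequence.

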10. SAFETY AND ADVERSE EVENTS

10.1 Potential Risks and Benefits

At screening, we will collect standardized historical, symptomatic, physical exam, and laboratory parameters to identify health conditions that represent risks for participation in the study's procedures. Chief among these would be unstable coagulopathies or anti-coagulant therapies that increase the risk of phlebotomy and lumbar puncture and unstable medical conditions.

10.1.1 Potential Risks

Nicotinamide Riboside: Nicotinamide riboside is well-tolerated in patients, with few adverse events reported in a minority (3.3%) of patients⁶:

- Mild nausea
- Mild skin rash
- Mild flushing/hot flashes
- Mild leg cramps
- Increased bruising

None of the reported adverse events led to discontinuation of NR during its intervention period.

Phlebotomy: The risks associated with having blood drawn include bruising and local discomfort. Rarely an infection may occur at this site, and if an infection does occur it will be treated by the study physician.

Magnetic Resonance Imaging: MRI is a safe procedure for subjects who do not have metal implants or other contraindications. Individuals who have electrically, magnetically, or mechanically-activated implants (such as heart pacemakers) or those who have clips on blood vessels in their brain will not be allowed to participate in the study due to risks associated with MRI scanning. The MRI will be operated in a manner accepted by the FDA. The protocol requires subjects to remain still within a relatively confined space during the scanning

Version:4.4

A Crossover, Randomized Block Sequence, Double-Blind, Placebo-Controlled Trial for Nicotinamide Riboside in Subjective Cognitive Decline and Mild Cognitive Impairment in Aging

session, and the scanner makes loud knocking and beeping sounds as it takes images. While subjects with severe claustrophobia are excluded from the study, some subjects may find the physical confinement or noise uncomfortable. Every effort will be made to enhance each subject's comfort level, and subjects will be given earplugs to reduce discomfort due to noise. If a subject notices any discomfort while in the MRI scanner, (s)he should notify the administrator immediately. If the discomfort cannot be stopped, the scanning session will be stopped. The MRI has the potential, during normal routine use, to cause localized warming of the skin and underlying tissues. Subjects should immediately inform the study staff if they experience discomfort due to warming of the skin and the procedure will be stopped.

Neurocognitive testing: The neurocognitive tests that will be administered to assess mental performance may be stressful and potentially cause anxiety, fatigue, and frustration. In our prior experience with similar protocols, risks have occurred infrequently and very few subjects have terminated testing. However, testing will be discontinued immediately upon any request by the subject to do so. With the evaluation of individuals with cognitive complaints, there is always the potential for a subject to enter the study with SCD and subsequently demonstrate a decline in cognitive performance throughout the course of the study to a level consistent with a diagnosis of MCI. If this occurs, a licensed clinician will meet with the subject and suggest that they see their primary care provider for further evaluation.

Daily Cognitive Exercises: The daily Lumosity (Lumos Labs, Inc.) brain exercises may be stressful, tedious, and potentially cause fatigue, and frustration. However, the program was designed to resemble games and the duration is short, so the likelihood of these potential risks is low.

Questionnaires: Questionnaires administered during the protocol may cause subjects to feel sad or upset about how their neurocognitive functioning affects their quality of life. Study staff is experienced with such evaluations and sensitive to these issues. Any question can be omitted per the subject's request.

Wrist Actigraphy: The wrist actigraph, the Fitbit Charge 3, may cause some minor discomfort due to prolonged wearing, but the risk of such discomfort will be minimized by ensuring the wristband fits the subject properly (e.g. is not too tight or does not cause irritation). If the subject does experience discomfort, another wristband will be ordered to try to eliminate the discomfort.

Lumbar puncture (LP): Pain may occur during the procedure. This is usually temporary, confined to the lower back, and minimized with the cutaneous and soft tissue administration of 1% lidocaine as a local anesthetic. Short-lived LP associated headaches occur in <1%-36% of subjects with an incidence that decreases with age^{45–47}. Less commonly, a persistent low-pressure headache may develop as a result of a post-LP CSF leakage. Lower rates of post-LP headache have been noted with the atraumatic (Sprotte) 24-gauge needle that will be used in this study⁴⁷. Potentially more serious, but very rare risks, include infection, damage to radicular nerves and bleeding into the lumbar CSF space. The risk of these procedure related complications is much less than 1%.

Videoconferencing: Visits that take place via videoconferencing may allow research staff to learn more about the subject's home and cohabitants than an office visit. The study team will use a secure Zoom

Version:4.4

A Crossover, Randomized Block Sequence, Double-Blind, Placebo-Controlled Trial for Nicotinamide Riboside in Subjective Cognitive Decline and Mild Cognitive Impairment in Aging

videoconferencing platform and conduct the visit in a private location to ensure personal information about the subject is kept confidential.

Other Risks: Reviewing health-related information might be stressful or make the subject feel uncomfortable. Subjects do not have to answer any questions they do not want to. In addition, there may be incidental medical findings as a result of the physical examination.

10.1.2 Known Potential Benefits

NR has been tested in a number of clinical trials in middle-aged and elderly patients and has shown to be well-tolerated. If successful, this trial will further understanding of the effects of NR on standard and personalized assessment of cognitive, neuropsychiatric, and everyday functioning in brain aging. This trial is also assessing multiple biomarkers in concert with clinical outcomes, which will provide a detailed understanding of NR activity and provide a well-curated data set for the Alzheimer's research community to improve our understanding of cognitive decline in aging and AD/ADRDs.

10.2 Data Security

10.2.1 Laptop computers and iPads

Subjects will be given the choice to use their personal computers or study-provided laptops to use for Lumosity cognitive exercises. Fitbit and Lumosity are web-based applications that require no PHI or personally identifiable information be entered into the system, so there are no additional data safety risks to the subject if they use their personal computers. Older adults may have difficulty adapting to new technologies, resulting in increased cognitive and perceptual demands⁴⁸. Because a major outcome of this trial is performance on computerized cognitive brain games, it is important that subjects' performance is not influenced by the novelty of the study laptop.

If a subject does not wish to use their personal computer, they will be provided with a study laptop. Study laptops will be registered under the Principal Investigator and no identifying information will be required to sign in. The study subject will be provided with a password that adheres to Partners password requirements to log in to the computer. We will also provide an information sheet with detailed instructions on how to use the laptop to complete study tasks in.

Subjects will sync Fitbit activity tracking through the Fitbit app downloaded to their personal mobile device by logging into the application with their provided, deidentified account. If a subject does not have a compatible smart phone, an iPad will be provided. The provided iPad will be a Partners device enrolled under Mobile Iron. The Fitbit app will be downloaded prior to distributing the iPad, and all other applications will be blocked from use.

10.2.2 Lumosity software

A Crossover, Randomized Block Sequence, Double-Blind, Placebo-Controlled Trial for Nicotinamide Riboside in Subjective Cognitive Decline and Mild Cognitive Impairment in Aging

Version:4.4

For the successful completion of this research study, Lumos Labs will provide de-identified user accounts to the principal investigator. The research team at MGH will be responsible for assigning these de-identified accounts to research participants, as they are enrolled in the trial. These accounts will have a generic date of birth and will not contain any personal health information or personally identifying information. Lumos Labs does not collect or store any personally identifying information of research participants. A copy of Lumos Labs Privacy Policy and Terms of Service will also be reviewed by the subject during the consenting process. By consenting to the study, the subject is also agreeing to these policies and terms.

Any record of cognitive exercises and assessment data provided by Lumos Labs to MGH will be restricted to data created through or generated by study subjects or study subjects access to or use of Lumosity and will not contain personal information of other Lumosity users. Lumos Labs will send data reports via email to the study staff in a CSV file which will be downloaded and stored on Partners compliant workstations.

10.2.3 Fitbit activity tracker

A study coordinator will create a unique, deidentified email and password combination to create an account on Fitbit.com. To create an account, the following information will be required: first and last Name (a de-identified placeholder name], date of birth (January 01, year of birth), gender, height, and weight. The subject will be given the associated account information so that they are able to login, sync their device, and use the Fitbit dashboard. The subject will be notified that the researcher will also have full access to their account and will be able to freely view and download the subject's data for research purposes. A copy of Fitbit's Privacy Policy and Terms of Service will also be reviewed by the subject during the consenting process. By consenting to the study, the subject is also agreeing to these policies and terms.⁴¹

After the subject has completed or if they are withdrawn from the study, their Fitbit account and all associated data will be deleted. However, prior to deleting the account, the de-identified study data will be downloaded and stored confidentially on Partner's computers for study purposes.

